Appendix C: Informed Consent (Template)

Appendix D: Case Report Forms (CRFs)

Protocol Synopsis**Protocol ID 4600**

Sponsor	Torax Medical, Inc. [name] [contact] [contact]
Study Title	RELIEF Study: A Prospective, Multicenter Study of Reflux Management with the LINX® System for Gastroesophageal Reflux Disease after Laparoscopic Sleeve Gastrectomy
Study Device	The LINX® Reflux Management System (LINX)
Indication	The LINX® Reflux Management System is a laparoscopic, fundic-sparing anti-reflux procedure indicated for patients diagnosed with Gastroesophageal Reflux Disease (GERD) as defined by abnormal pH testing, and who are seeking an alternative to continuous acid suppression therapy (i.e. proton pump inhibitors or equivalent) in the management of their GERD.
FDA Approval	March 22, 2012
Study Design	An observational, multicenter, single-arm study with prospective enrollment.
Purpose	To evaluate the safety and efficacy of LINX for its approved indication in patients who have had prior gastric surgery, specifically, laparoscopic sleeve gastrectomy (LSG).
Objective	To confirm safety and efficacy after LSG in patients indicated for LINX is similar to the outcomes that formed the basis for Premarket Approval (PMA) to support modification of the current labeling with a statement that prior gastric surgery with LSG has been evaluated for safety and efficacy.
Number of Subjects	Up to 30 subjects
Study Centers	Up to 12 implanting sites in the U.S.
Study Duration	36 months (24-month enrollment period + 12-month follow-up period)
Evaluation of Safety	Rate of serious device and procedure related adverse events assessed by reporting all adverse events and by estimating the rate of serious device and procedure related adverse events through 12 months post implantation. Safety will also be evaluated by endoscopy to assess the mucosa and abdominal/chest X-ray evaluations to verify device location at 12 months post implantation.
Evaluation of Efficacy	Percentage of subjects reporting at the 12-month follow-up: 
• Normalization of total distal acid exposure (% total time pH<4) or at least 50% reduction in total distal acid exposure compared to baseline• At least 50% reduction in total GERD-HRQL score compared to baseline (off PPIs)• At least 50% reduction in average daily PPI dosage compared to baseline
Study Management	Torax Medical Inc. or Designate

Schedule of Data Collection

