6.0 SELECTION AND WITHDRAWAL OF SUBJECTS

6.1 INCLUSION CRITERIA

Subjects included in the study must meet all the following criteria:

1. Age >22 years
2. Laparoscopic sleeve gastrectomy (LSG) for obesity ≥ 12 months prior to proposed device implantation date.
3. Subject is a surgical candidate, i.e. is able to undergo general anesthesia and laparoscopic surgery.
4. Documented typical symptoms of GERD for longer than 6 months (regurgitation or heartburn which is defined as a burning epigastric or substernal pain which responds to acid neutralization or suppression).
5. Subject requires daily proton pump inhibitor or other anti-reflux drug therapy.

6. Total distal ambulatory esophageal pH must meet the following criteria: pH <4 for $\geq 4.5\%$ of the time. Note: Subjects shall have discontinued any GERD medications for at least 7 days prior to testing, with the exception of antacids up to the morning of testing.
7. Subjects with symptomatic improvement on PPI therapy demonstrated by a GERD-HRQL score of ≤ 10 **on** PPI and ≥ 15 **off** PPI, or subjects with a >6 point improvement when comparing their **on** PPI and **off** PPI GERD-HRQL scores.
8. GERD symptoms, in absence of PPI therapy (minimum 7 days).
9. If the subject is of child bearing potential must have a negative pregnancy test within one week prior to implant and must agree to use effective means of birth control during the course of the study.
10. Subject is willing and able to cooperate with follow-up examinations
11. Subject has been informed of the study procedures and the treatment and has signed an informed consent form.

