6-Month	
 • GERD-related medication use within the last 30 days • GERD-HRQL (off PPIs) and Foregut Symptoms Questionnaire (off PPIs) • Device and/or procedure related adverse events

[figure not shown]
Visit	Assessments/Data to be Collected
12 Month Follow-up	
 • Height and weight • GERD-HRQL (off PPIs) and Foregut Symptoms Questionnaire (off PPIs) • GERD-related medication use within the last 30 days • Esophageal pH testing (off PPIs) • Manometry/motility • Endoscopy • Barium esophagram and upright Bi-Planar X-Rays • Device and/or procedure related adverse events

The data collection window for each visit is outlined in **Table 4**. The 2-week follow-up visit is +/- 7 days from the anniversary of the implant procedure. The 3-month follow-up visit is +/- 14 days from the anniversary of the implant procedure. The 6-month follow-up visit is +/- 30 days from the anniversary date of the implant procedure. The 12-month follow-up visit is +/- 60 days from the anniversary date of the implant procedure.

Table 4: Follow-up Windows

Visit	Follow-up Window
2-week (+7 days)	7—21 days
3 months (+14 days)	76–104 days
6 months (+30 days)	150-210 days
12 Months (+60 days)	305-425 days

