10.1.3 USE OF PPIS

Subject's average daily dose of PPI will be evaluated. The subject's baseline average daily dosage will serve as the control and be compared to the subject's average daily dosage 12 months post-procedure.

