1.2 Study Design

This is an observational, multicenter, single-arm study with prospective enrollment. Based on the observational status of the study, no formal statistical hypothesis tests will be conducted. Up to 30 subjects meeting the eligibility requirements will be implanted with LINX and followed through 12-months after implant. Up to twelve clinical sites will enroll subjects. Safety evaluations will be ongoing throughout the duration of the study, starting at the implant procedure. Efficacy endpoints will be evaluated at the 12-month visit.

Safety will be assessed by evaluating device and/or procedure related adverse events, perioperative complications, device malfunctions, device removals, and hospital readmissions experienced by subjects post-LINX implant out to 12 months. Esophageal anatomy and functionality will be monitored by performing manometry and barium esophagram at 12-months post-implant. This will allow for identification of any abnormal or atypical findings. Further, device migration will be assessed by confirming device position at the gastroesophageal junction (GEJ) by obtaining upright, bi-plane X-rays and device erosion will be assessed by performing endoscopy at the 12-month visit.

Efficacy will be assessed by evaluating the percentage of subjects reporting at the 12-month follow-up:

- Normalization of total distal acid exposure time or at least 50% reduction in total distal acid exposure time compared to baseline.
- >50% reduction in total GERD-HRQL score compared to baseline (off PPIs).
- >50% reduction in average daily PPI dosage compared to baseline.

2 Treatment Assignment

This is a prospective, multicenter, single-arm, observational study, where subjects serve as their own control.

3 Randomization and Blinding Procedures

This is an observational, single-arm study. No randomization will occur, and no blinding procedures will be needed.

4 Interval Windows

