8.5.3 Use of PPIs

Subject's average daily dose of PPI will be evaluated. The subject's baseline average daily dosage will serve as the control and be compared to the subject's average daily dosage 12 months post-procedure.

The proportion of subjects with at least 50% reduction in daily PPI use from baseline at 12 months will be reported. In addition, a two-sided 95% CI will be provided for the proportion of success (>=50% reduction achieved).

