Number of Subjects with at Least 50% Reduction on GERD-HRQL				xx (xx.x%)

Denominator and percentages are based on subjects completed baseline and 12 months follow-up per protocol requirements.

[1] % Successful is defined as number of subjects meeting the success criterion of at least 50% reduction on GERD-HRQL at 12 months follow-up compared to baseline off PPI.

Table 15
 Daily PPI Medication Use from Baseline to 12 Months
 Full Analysis Set

Parameter	Baseline	12 Months Follow-Up	Change from Baseline to 12 Months Follow-Up	% Successful at 12 Months Follow-Up [1]
PPI Use (mg) [2]				
n	xx	xx	xx	
Mean (SD)	xx.x (xx.x)	xx.x (xx.x)	xx.x (xx.x)	
Median (Min, Max)	xx.x (xx, xx)	xx.x (xx, xx)	xx.x (xx, xx)	
95% Confidence Interval			(xx.xxx, xx.xxx)	
Number of Subjects with at Least 50% Reduction in Daily Use				xx (xx.x%)

Denominator and percentages are based on subjects completed baseline and 12 months follow-up.

[1] % Successful is defined as number of subjects meeting the success criterion of at least 50% reduction in daily PPI use from baseline at 12 months.

[2] PPI Use is defined by the evaluation of subject's daily dose of PPI.

<Programming note those PPI administrated as PRN will not be included in daily dose calculation..>

Table 16
 Abdominal/Chest X-Ray at 12 Months Follow-Up
 Full Analysis Set

Characteristic	12 Months Follow-Up (N = ##)
Is the LINX device at the gastroesophageal junction?	
Yes	xx.x (xx.x)
No	xx.x (xx.x)
Any Evidence of Device Migration?	
Yes	xx (xx.x%)
No	xx (xx.x%)

Denominator and percentages are based on subjects with non-missing data.

Table 17
 Foregut Symptoms Questionnaire by Visit (Off PPI)
 Full Analysis Set

Characteristic	Baseline (N = ##)	3 Months Follow-Up (N = ##)	6 Months Follow-Up (N = ##)	12 Months Follow-Up (N = ##)
Regurgitation Frequency				
None	xx (xx.x%)	xx (xx.x%)	xx (xx.x%)	xx (xx.x%)
Mild	xx (xx.x%)	xx (xx.x%)	xx (xx.x%)	xx (xx.x%)
Moderate	xx (xx.x%)	xx (xx.x%)	xx (xx.x%)	xx (xx.x%)
Severe	xx (xx.x%)	xx (xx.x%)	xx (xx.x%)	xx (xx.x%)
Lung Problems				
None	xx (xx.x%)	xx (xx.x%)	xx (xx.x%)	xx (xx.x%)
Recurrent cough	xx (xx.x%)	xx (xx.x%)	xx (xx.x%)	xx (xx.x%)
Nocturnal cough	xx (xx.x%)	xx (xx.x%)	xx (xx.x%)	xx (xx.x%)
Recurrent pneumonitis	xx (xx.x%)	xx (xx.x%)	xx (xx.x%)	xx (xx.x%)
Asthma	xx (xx.x%)	xx (xx.x%)	xx (xx.x%)	xx (xx.x%)
Change of voice	xx (xx.x%)	xx (xx.x%)	xx (xx.x%)	xx (xx.x%)
Other	xx (xx.x%)	xx (xx.x%)	xx (xx.x%)	xx (xx.x%)
Ability to Vomit				

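### SAP Table 15 leaves as-needed (PRN) PPI out of the daily dose, so a near-daily PPI user can count as a success on the average daily dosage endpoint

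*SAP*

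**What the plan says.** The Protocol Synopsis lists the endpoint as "At least 50% reduction in average daily PPI dosage compared to baseline", reported as the percentage of subjects who reach it at 12 months. Protocol 5.2 repeats it. Protocol 10.1.3 names the analysis variable: the subject's "average daily dose of PPI will be evaluated", with baseline as the control. SAP 1.2 carries the endpoint over as a "50% reduction in average daily PPI dosage compared to baseline". SAP 8.5.3 adds: "The proportion of subjects with at least 50% reduction in daily PPI use from baseline at 12 months will be reported", with a two-sided 95% CI. None of these places mentions PRN use.

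The exclusion appears only in the programming note under SAP Table 15: "those PPI administrated as PRN will not be included in daily dose calculation". It sets no limit on frequency or amount and gives no reason, and no analysis that counts PRN use accompanies it. Footnote [2] of the table says only that PPI use means the daily dose. The denominator footnote reads "Denominator and percentages are based on subjects completed baseline and 12 months follow-up", so PRN users stay in the denominator. The note does not say whether a PRN-only subject has a dose of zero or a missing dose.

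Two further places bear on the size of the problem. Protocol 6.1, item 5, requires: "Subject requires daily proton pump inhibitor or other anti-reflux drug therapy". Protocol Table 3 collects, at each of the 3-, 6- and 12-month visits, "GERD-related medication use within the last 30 days".

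**The concern.** An average daily dose differs from a scheduled dose exactly when use is irregular. Leaving out PRN use therefore changes what is measured, from PPI consumed to PPI taken on a schedule, while the table still presents the result as the subject's daily dose. A move from scheduled to PRN use is a plausible partial response in this study. Under the note, such a subject contributes 0 mg at 12 months however often the drug is taken.

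This is one of three efficacy endpoints in a study meant to support a labeling statement (Protocol 3.0, SAP 1.1). The study has no hypothesis and no success threshold, so the estimate and its interval are the product. What is at stake is a biased estimate, not a reversed decision.

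**Working it through.** There is no plan figure to reproduce: SAP 7 reports no sample size calculation, and neither document gives an expected PPI success rate.

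**Inputs.** Success is a reduction of at least 50% (Protocol 5.2, SAP 8.5.3, Table 15; the SAP 1.2 bullet prints a strict greater-than sign). The recall period is 30 days (Protocol Table 3). Planned n is up to 30 (SAP 1.2). Assumptions: r is the dose on a PRN day divided by the baseline daily dose, d is the number of PRN days, and PRN-only use scores as 0 mg.

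**1. Scheduled PPI at baseline, PRN only at 12 months.** True reduction = 1 − r × d/30. Scored reduction = 100%. The subject is misclassified when r × d/30 > 0.5.
- r = 1: 15 days gives 1 − 15/30 = 50.0%, a true success. 16 days gives 46.7% and 30 days gives 0%, so 16 to 30 days is misclassified.
- r = 0.75: 21 days gives 1 − 15.75/30 = 47.5% and 30 days gives 25.0%, so 21 to 30 days is misclassified.
- r = 0.5: 30 days gives exactly 50.0%, so nobody is misclassified.
- r = 2: 10 days already gives 1 − 20/30 = 33.3%, a failure.

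The 12-month questionnaires and pH test require at least 7 days off GERD medication. If 7 such days fell inside the recall period and were not counted, the divisor would be 23. Misclassification would then start at 12 days for r = 1 (1 − 12/23 = 47.8%) and at 16 days for r = 0.75 (1 − 12/23 = 47.8%).

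**2. Scheduled plus PRN at 12 months.** Take a scheduled dose at half of baseline, plus PRN at half of baseline on 5 of 7 days. True: 1 − (0.5 + 0.5 × 5/7) = 14.3%. Scored: 1 − 0.5 = 50%, a success under the at-least rule.

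**3. The opposite direction.** Take baseline scheduled 1 unit plus PRN 1 unit on 15 of 30 days, which is 1.5 units, and scheduled 0.75 unit at 12 months. True: 1 − 0.75/1.5 = 50%, a success. Scored: 1 − 0.75/1 = 25%, a failure.

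**4. Effect on the rate.** One subject is worth 1/30 = 3.3 points, or 1/20 = 5.0 points at an assumed 20 evaluable subjects. SAP 8.8 records lower than anticipated follow-up, which is why a smaller n is shown. The counts below are illustrative. The intervals are Clopper-Pearson, which the SAP names for the pH endpoint only.
- n = 30: 24/30 = 80.0% (61.4 to 92.3) becomes 23/30 = 76.7% (57.7 to 90.1) with one subject reclassified, and 21/30 = 70.0% (50.6 to 85.3) with three.
- n = 20: 16/20 = 80.0% (56.3 to 94.3) becomes 13/20 = 65.0% (40.8 to 84.6) with three.

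**5. Bounds when PRN days are unknown.** Take baseline scheduled 1 + PRN 1, and 12 months scheduled 0.5 + PRN 0.5. Zero PRN days at both visits gives 1 − 0.5/1 = 50%. Every day at both gives 1 − 1/2 = 50%. Zero days at baseline with every day at 12 months gives 1 − 1/1 = 0%. Bounds that set both visits to the same extreme would miss this failure, so the extremes must be crossed between visits.

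**The case against.** The strongest reply is that the rule is written openly, applies as worded to both visits, and sits in a table titled as daily medication use. Relabelling the row as scheduled dose and adding a row that counts PRN would remove the wording mismatch. That is fair as to transparency, but the endpoint named in the Protocol would then have only a secondary row.

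Other outputs also help. Table 3 shows who is currently taking a PPI at each visit, and Listings 10 and 17 list GERD medications. They may let a reader see users whom Table 15 sets to 0 mg, but they do not correct the Table 15 rate.

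The 0 mg reading is not stated. SAP 8.9 summarises observed data only. If a PRN-only dose were treated as missing while the subject stayed in the denominator, that subject would not be a success and the bias would reverse. A note about what enters a dose calculation reads more naturally as zero, but the ambiguity is real.

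A reader might infer that the rule can only inflate the success rate. The documents do not support that: step 3 shows a true success scored as a failure. Inclusion item 5 makes PRN-only PPI use at baseline less likely, but does not rule out PRN on top of a scheduled dose.

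A reader might also take a subject who succeeds in Table 15 and is marked No in Table 29 as proof of error. It is not. Table 29 measures discontinuation, so a subject who cuts a scheduled dose by 60% would differ between the two tables by design.

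**Conclusion.** The Table 15 note conflicts with the endpoint as both documents define it, and nothing elsewhere in the plan resolves the conflict. On the 0 mg reading it gives wrong classifications: at the full baseline dose per PRN day, 16 to 30 days of use out of 30 is a true reduction of 46.7% to 0% scored as 100%. Where baseline PPI is entirely scheduled, the error can only raise the success rate. Where baseline includes PRN on top of a scheduled dose, it can lower it.

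The existence of the mismatch is certain; its net effect is not. The number of affected subjects is not in the documents and could be zero, and at half the baseline dose per PRN day or less no PRN-only subject is misclassified. Each affected subject moves the rate by 3.3 points at n=30. A reader might infer that the study's conclusion would change, but there is no threshold to cross. The point should be fixed because a stated rule misclassifies subjects and is cheap to change.

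**What to change.** In SAP 8.5.3 and Table 15:

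(a) Delete the PRN exclusion. Count PRN PPI as dose per day of use × days taken ÷ days in the reference period, in the same way at both visits. Define that period, and say whether days off medication for testing count; Protocol Table 3 states the 30-day recall for follow-up but no period for baseline.

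(b) Where PRN days were not recorded, report lower and upper bounds for the success rate, each with its 95% CI, as a stated exception to SAP 8.9. For the lower bound, set unknown baseline PRN days to 0 and unknown 12-month PRN days to every day. For the upper bound, do the reverse. Hold a subject fixed only if the classification is the same in both. If the 12-month PRN dose itself was not recorded, class the subject as a non-responder in the lower bound. If the baseline PRN dose was not recorded, class the subject as a responder in the upper bound.

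(c) Show the PRN-excluded result as a sensitivity row labelled as scheduled PPI dose only.

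(d) Report subjects with zero baseline PPI dose separately, for example those on other anti-reflux therapy only, because their percent reduction is undefined.

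The cost is SAP wording and limited reprogramming of one table. The case report forms are not in the text available, so how fully PRN days and dose were recorded is unknown; (b) allows for gaps in either. The downside is that the reported rate may change, usually downward, or become a range.

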10.2 SAFETY

Safety will be assessed by the rate of (number and percentage of subjects experiencing) device and/or procedure related adverse events after LINX

placement out to 12 months. Esophageal anatomy and functionality will be monitored by performing manometry and barium esophagram at 12-months post-implant. This will allow for identification of any abnormal or atypical findings. Further, device migration will be assessed by confirming device position at the GEJ by obtaining upright, bi-plane X-rays and device erosion will be assessed by performing endoscopy at the 12 month visit. Incidence of device migration and erosion will be compared to current incidence rates (i.e. zero documented incidents of device migration and a low but established occurrence of esophageal erosions) to assess concurrence of the safety profile of study subjects to that of patients without a prior LSG.

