Interval windows are not defined for the purpose of analysis in this study outside of the visit windows that are provided in the Study Schedule and Assessments in the final protocol. There will be no assigning of observations to time points outside of the visit to which they are recorded in the electronic Case Report Forms (eCRFs). Data collected in Unscheduled Visits forms will be listed as such. Observations collected outside of the 12-month protocol-specified visit window may be still be included in the analysis of primary effectiveness and safety endpoints since the device under study is an implant and longer term follow-up (i.e. beyond 12-months) is still considered informative towards evaluating the overall benefit-risk profile of the device in subjects with prior LSG surgery.

5 Levels of Significance

No formal statistical hypotheses are specified for this study. For continuous efficacy parameters, the p-value for a one sample, paired t-test to test if there is statistical evidence that the change from baseline is not equal to zero will be given. All estimation of endpoints will be performed using 95% confidence intervals.

6 Analysis Sets

All subjects who meet the eligibility criteria, provide informed consent, complete baseline assessments and undergo the LINX procedure will represent the study population for analysis. This set of subjects will be labeled as Full Analysis Set (FAS). This set of subjects will be identified by having answered “Yes” to the question “Was the LINX device implanted?” on the Implant Data eCRF.

7 Sample Size Justification

No formal sample size calculation has been performed for this study. The sample size planned for the study is up to 30 eligible subjects recruited from 12 clinical sites and no site will enroll more than 6 subjects without prior written approval provided by the Sponsor. No formal hypothesis has been tested in this study; thus, the sample size is not statistically sized, but rather is considered

sufficient for a descriptive summary of LINX performance for subjects who have had prior gastric surgery with LSG through confidence interval estimation and evaluation of safety and efficacy.

8 Analyses to be Conducted

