8.6 Safety Analyses

Safety will be assessed by the rate of AEs and SAEs (number and percentage of subjects experiencing). Similar summaries will also be provided for AEs and SAEs related to the study device, as well as for AEs and SAEs related to the study procedures. Related events are those where the event relatedness is indicated as Yes/Probably/Possibly, or Unknown. Esophageal anatomy and functionality will be monitored by performing manometry and barium esophagram at 12-months post-implant. A summary and change from baseline of manometry and motility results will be provided which includes LES length, LES residual pressure, LES intra-abdominal length, LES basal mean pressure, percent peristaltic sequences, distal amplitude, distal contractile integral, percent ineffective swallows, and percent fragmented swallow. Count and percentages will be provided for barium esophagram in the number of subjects who have normal swallow function, number of subjects who have a dilated proximal pouch, number of subjects who have evidence of a hiatal hernia, and if any abnormalities occurred. This will allow for identification of any abnormal or atypical findings. Further, device migration will be assessed by confirming device position at the GEJ by obtaining upright, bi-plane X-rays and device erosion will be assessed by performing an endoscopy at the 12 months visit.

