8.8 Plans for Interim Analysis

No formal interim analyses were planned in the protocol that would have the intent of altering the study design. However, given the lower than anticipated follow-up that was initially observed in the study, reviews of data for completeness of endpoint data were performed when the initial study enrollment of 30 subjects was completed. The intent of these analyses and data reviews were to attempt to assess the overall completeness of the dataset.

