8.9 Handling of Missing Data

All summaries will be performed only on enrolled subjects and only observed data will be summarized. There will be no imputation of data for early terminated subjects or for missing data within the database.

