Yes	xx (xx.x%)	xx (xx.x%)	xx (xx.x%)	xx (xx.x%)
No	xx (xx.x%)	xx (xx.x%)	xx (xx.x%)	xx (xx.x%)
No need to vomit	xx (xx.x%)	xx (xx.x%)	xx (xx.x%)	xx (xx.x%)
Ability to belch				
Yes	xx (xx.x%)	xx (xx.x%)	xx (xx.x%)	xx (xx.x%)
No	xx (xx.x%)	xx (xx.x%)	xx (xx.x%)	xx (xx.x%)

Denominator and percentages are based on subjects with non-missing data.

Table 18
 Regurgitation Severity Elimination from Severe and Moderate (Off PPI)
 Full Analysis Set

Change from Baseline	3 Months Follow-Up (N = ##)	6 Months Follow-Up (N = ##)	12 Months Follow-Up (N = ##)
Eliminate severe (to moderate, mild or none) [1]	xx (xx.x%)	xx (xx.x%)	xx (xx.x%)
Eliminate moderate (to mild or none) [2]	xx (xx.x%)	xx (xx.x%)	xx (xx.x%)

Column header counts represent the number of subjects who complete the FSQ form at the given visit.

[1] Percentages are calculated using the number of subjects with severe regurgitation at baseline and who complete the FSQ form at the given visit.

[2] Percentages are calculated using the number of subjects with moderate regurgitation at baseline and who complete the FSQ form at the given visit.

Table 19
 Regurgitation Frequency Summary (Off PPI)
 Full Analysis Set

Frequency	Baseline (N = ##)	3 Months Follow-Up (N = ##)	6 Months Follow-Up (N = ##)	12 Months Follow-Up (N = ##)
Regurgitation (times/week)				
n	xx	xx	xx	xx
Mean (SD)	xx.x (xx.x)	xx.x (xx.x)	xx.x (xx.x)	xx.x (xx.x)
Median (Min, Max)	xx.x (xx, xx)	xx.x (xx, xx)	xx.x (xx, xx)	xx.x (xx, xx)

Table 20
Adverse Events Summary
Full Analysis Set

Adverse Event Category	Number of Subjects (N = ##)	Number of Events
Any Adverse Events	xx (xx.x%)	xx
Serious Adverse Events	xx (xx.x%)	xx
AE related (Yes/Probably/Possibly or Unknown) to Study Device	xx (xx.x%)	xx
AE related (Yes/Probably/Possibly or Unknown) to Implant Procedure	xx (xx.x%)	xx
SAE related (Yes/Probably/Possibly or Unknown) to Study Device	xx (xx.x%)	xx
SAE related (Yes/Probably/Possibly or Unknown) to Implant Procedure	xx (xx.x%)	xx

All percentages are calculated using the number of subjects in the FAS as the denominator.

Table 21
All Adverse Events
Full Analysis Set

Adverse Event Category	Number of Subjects (N = ##)	Number of Events
Total	xx (xx.x%)	xx
Achalasia	xx (xx.x%)	xx
Allergic reaction	xx (xx.x%)	xx
Anaphylaxis	xx (xx.x%)	xx
....	xx (xx.x%)	xx

All percentages are calculated using the number of subjects in the FAS as the denominator.

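### The 12-month safety rate is estimated only as a crude percentage of all implanted subjects, so it can understate the risk if subjects leave early

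*SAP*

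**What the plan says.** The Protocol Synopsis evaluates safety by reporting all adverse events and by "estimating the rate of serious device and procedure related adverse events through 12 months post implantation". Protocol 10.2 gives the form of the rate, which it also ends at 12 months: "Safety will be assessed by the rate of (number and percentage of subjects experiencing) device and/or procedure related adverse events after LINX". SAP 8.6 keeps that form: "Safety will be assessed by the rate of AEs and SAEs (number and percentage of subjects experiencing"). It mentions no time at risk, censoring or minimum follow-up.

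The footnote to Tables 20 and 21 sets the denominator: "All percentages are calculated using the number of subjects in the FAS as the denominator". Under SAP section 6 the FAS consists of eligible, consented subjects with baseline assessments who "undergo the LINX procedure will represent the study population for analysis". They are identified by the implant question on the eCRF, and no follow-up is required.

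Three other provisions bear on the rate:
- SAP 8.8 reports data reviews made "given the lower than anticipated follow-up that was initially observed in the study", without a number.
- SAP 8.9 summarises observed data only: "There will be no imputation of data for early terminated subjects or for missing data within the database".
- SAP section 4 states: "Observations collected outside of the 12-month protocol-specified visit window may be still be included in the analysis of primary effectiveness and safety endpoints".

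SAP section 5 promises 95% confidence intervals for endpoint estimates, but the shells of Tables 20 and 21 show none.

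**The concern.** A rate through 12 months is a statement about risk over a fixed period. Dividing by everyone implanted estimates that risk without bias only if every subject without an event was watched for the whole period. A subject last contacted at two weeks, with nothing recorded, carries the same weight in Table 20 as one followed event-free for a year.

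This matters because the stated objective is to confirm that safety after LSG is similar to the outcomes behind the PMA, in support of a label change. With at most 30 subjects, the upper confidence limit is the most informative safety figure, and it depends directly on how many subjects were actually observed. Erosion is looked for by endoscopy at 12 months, so early loss can remove exactly the observation that would reveal a late event.

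**Working it through.** The documents give no safety rate, event timing or loss rate, so there is no figure of the plan to reproduce. N = 30 comes from SAP section 7 and day 305 is the start of the 12-month window (Protocol Table 4). Every risk, loss and timing below is an assumption, used only to show the range.

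**1. Constant hazard, loss spread evenly over the year.** Let F be the true 12-month risk, d the share lost and λ = −ln(1 − F). A lost subject has on average accrued a risk of 1 − F/λ. With F = 0.10, λ = 0.1054 and 1 − 0.10/0.1054 = 0.051. The expected Table 20 percentage is (1 − d)·F + d·0.051:
- d = 10%: 9.5%
- d = 20%: 9.0%
- d = 30%: 8.5%
- d = 40%: 8.0%

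The relative understatement is about 5% to 20%.

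**2. All loss at month 3.** Let e be the share of the risk that falls before loss, with the remainder even over 12 months (a quarter of it accrued by month 3). The expected percentage is (1 − d)·F + d·[F·e + F·(1 − e)·0.25]. With F = 10% and d from 10% to 40%:
- e = 0: 9.25% to 7.0%
- e = 0.8: 9.85% to 9.4%
- e = 1: 10.0% throughout, no bias

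**3. Crude against Kaplan-Meier.** Take 30 implanted, events at months 1, 5 and 9, and k event-free subjects lost at month 3. For k = 9 the risk sets are 30, 20 and 19, so the 12-month risk is 1 − (29/30)(19/20)(18/19) = 13.0%.

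| k lost | Table 20 | Kaplan-Meier | Event or full follow-up | All lost had an event |
|---|---|---|---|---|
| 3 | 10.0% | 10.8% | 3/27 = 11.1% | 6/30 = 20% |
| 6 | 10.0% | 11.7% | 3/24 = 12.5% | 9/30 = 30% |
| 9 | 10.0% | 13.0% | 3/21 = 14.3% | 12/30 = 40% |
| 12 | 10.0% | 14.7% | 3/18 = 16.7% | 15/30 = 50% |

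The Table 20 figure does not move with the loss. The fourth column runs above Kaplan-Meier because it discards the event-free time of those lost.

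**4. No events.** The exact two-sided 95% upper limit is 1 − 0.025^(1/n): 11.6% for 0/30 and 16.8% for 0/20.

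**5. The opposite direction.** If one further subject had a first event after 12 months and it were counted under SAP section 4, the crude figure would go from 3/30 = 10.0% to 4/30 = 13.3%.

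**The case against.** Dividing by all treated subjects is a common convention for adverse event tables, and Protocol 10.2 itself defines the rate as a number and percentage of subjects. That is fair, and it is why the FAS tables should stay. What remains is that this is the only visible estimate of a rate tied to 12 months.

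A reader might infer that Table 20 breaches SAP 8.9 by imputing no event. The documents do not support that: counting recorded events per implanted subject uses observed data and fills in no value. Nor do the different denominators in the imaging and efficacy tables show a contradiction. A 12-month test can be missing for a subject, whereas adverse events are collected from implant onward.

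A reader might also take SAP 8.8 as proof that safety follow-up was poor. It says only that follow-up was initially lower than anticipated, and that the reviews concerned completeness of endpoint data. Protocol 7.0 allows follow-up by telephone apart from the tests, so a missed pH study or endoscopy need not mean lost safety contact.

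Events before loss stay in the numerator. Withdrawal for an adverse event requires an adverse event form (Protocol 11.10), and explants are picked up from two forms. Table 1 and Listings 3, 20 and 22 will show withdrawals, visits and events, but they do not turn these into a 12-month risk.

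Finally, part of the SAP appendix, apparently the shells between Tables 21 and 29, was not in the text available for this review. A time-based table there cannot be excluded. The visible remnant covers only time to explant, and SAP 8.6 describes no time-at-risk estimate.

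**Conclusion.** The point holds and should be fixed. The plan promises a 12-month rate but visibly specifies only a crude percentage over all implanted subjects. That percentage understates the 12-month risk if subjects without a recorded event are lost before 12 months.

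The size cannot be computed from the documents. Under the assumptions in step 1 the understatement is 5% to 20% in relative terms. It falls to nothing if related events cluster around surgery and grows if loss is early and events are late. It is tempting to say that the rate is understated by one third, as when 2/30 = 6.7% is set against 2/20 = 10.0%. That needs a third of subjects lost almost at once and no event among them while they were observed. Nothing in the documents supports so extreme a case. The net direction is not certain either, because events from beyond the window may be included and there is no firm 12-month cut.

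**What to change.** Keep the FAS counts in Tables 20 and 21. In SAP 8.6, name the study day that closes the 12 months for events counted in the rate, and list later events separately. For related SAEs, related AEs and explants, add one table with:

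- (a) the number of subjects with safety contact, including by telephone, to at least day 305;
- (b) the 12-month Kaplan-Meier cumulative incidence with 95% CI, censored at last safety contact, quoted as the rate through 12 months. Say explicitly how this applies to explanted subjects, who may leave after the monitoring period in Protocol 11.9;
- (c) if there are no events, the exact Clopper-Pearson upper limit on the number followed to day 305, since the usual Kaplan-Meier interval is then degenerate;
- (d) as a sensitivity figure only, the proportion among subjects with an event or complete follow-up, with a note that it tends to run high.

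The cost is a paragraph and one table. Adverse event, visit and withdrawal data are already listed, and implant and explant dates are already programmed. That event onset and last contact dates are also held is likely, but the CRFs were not available to confirm it. The downside is a somewhat less favourable rate and upper limit.
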